9.4.3 Pharmacokinetics

Please refer to [Section 9.3.1](#) for details.

9.6 (Other) Safety analyses

Not applicable

9.7 Other analyses

No other analyses are planned.

9.8 Interim analysis

An interim analysis is planned when approximately 8 patients complete Day 14 visit. The study will continue to recruit participants while this interim analysis is being completed up to a cap of 12 participants. The study will continue without modification if a similar PK profile of TIN816 to that in the healthy volunteers (CTIN816A02101) is confirmed. Otherwise, the study may be amended with options of additional arms for testing a higher dose, multiple bolus doses, extended infusion dosing regimens or combination of bolus dose and extended infusion. The total sample size may increase to provide adequate PK data after dose level and/or dose regimens are changed. In the circumstance that the data from the first IA does not provide sufficient PK data to support the phase 2b, an additional IA will be added when all 20 patients complete Day 14 visit.

9.9 Sample size determination

The sample size was determined to achieve a target margin of error of the mean for PK parameters C_{max} and AUC_{inf} . The assumption of geometric coefficient of variation (GCV) rate was referenced from FIH study (CTIN816A02101) interim safety report.

9.9.1 Primary endpoint(s)

The proposed sample size of 15 participants in TIN816 study treatment arm is sufficient to achieve a target margin of error not larger than 15% of the geometric mean (half-width of a 2-sided 95% confidence interval for the PK parameters) assuming geometric coefficient of variant (GCV) is 0.25 in AUC_{inf} or C_{max} . It will also be able to exclude a 1.5-fold change in AUC_{inf} or C_{max} assuming GCV increased variability of 0.75.

Different GCV rates and corresponding precision of confidence interval are shown in below table.

Table 9-2 Sensitivity of confidence interval precision to change in assumption for GCV rate

GCV rate *	Width of 95% confidence interval
0.25	[GCV mean/1.15, GCV mean x 1.15]
0.50	[GCV mean/1.31, GCV mean x 1.31]
0.75	[GCV mean/1.47, GCV mean x 1.47]

*GCV mean of AUC_{inf} and C_{max} for 2 mg/kg are 8% and 22%, respectively in FIH study (CTIN816A02101) interim safety reports

10 Supporting documentation and operational considerations

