2.2 Background

During sepsis, a dysregulated host response to infection leads to a life-threatening multi-organ dysfunction. Sepsis is a leading cause of death and a major public health problem that affects millions of patients worldwide every year (Fleischmann et al., 2016, Rudd et al., 2020). In the United States (US) alone, an estimated 1.7 million adults present to hospital each year with sepsis with up to 270,000 deaths resulting (Rhee et al., 2017). An aging population and an increase in underlying comorbidities have led to continuous growth in the incidence of sepsis (Mayr et al., 2014).

Approximately 90% of sepsis is caused by bacterial infection and 40-60% of septic patients experience sepsis-associated acute kidney injury (SA-AKI) (Liu et al., 2020, Yu et al., 2021). Acute kidney injury (AKI) refers to an abrupt decrease in kidney function, resulting in the retention of urea and other nitrogenous waste products and in the dysregulation of extracellular volume and electrolytes. It is estimated that ~813,000 patients suffer from SA-AKI in the US, ~793,000 in urban China, ~232,000 in Japan and ~79,000 in Germany (Fleischmann-Struzek et al., 2018, Peters et al., 2018, Tian et al., 2019, Imaeda et al., 2021).

Development of AKI in patients with sepsis is associated with significantly increased mortality rate of up to 65%, and survivors are at significantly increased risk of developing chronic kidney disease (CKD) and kidney failure, resulting in a significant health and financial burden for both patient and society (Peerapornratana et al., 2019, Chua et al., 2020, Liu et al., 2020).

SA-AKI is a multifactorial syndrome with inflammatory, nephrotoxic, and ischemic insults occurring simultaneously with other pathophysiological responses rapidly leading to kidney impairment. Over the last 30 years, there were a considerable number of potential drug targets and the development of new therapies to treat sepsis and/or AKI. Attempts were primarily focusing on improving hemodynamics, reducing oxidative stress, and blocking hyper-inflammatory response; however, all of which have failed in clinical trials (Cohen et al., 2015, Kellum et al., 2021). As a result, there are currently no specific pharmacological agents available for the treatment of SA-AKI. Management of patients with SA-AKI relies mainly on targeted antibiotics and supportive treatment including fluid resuscitation, vasoactive agents and renal replacement therapy (RRT).

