4.7 End of study definition

The end of the study is defined as the date of the last visit of the last participant in the study.

Study completion is defined as when the last participant finishes their last study visit and any repeat assessments associated with this visit have been documented and followed-up appropriately by the investigator.

5 Study population

The study population will be comprised of hospitalized male and female patients with a diagnosis of sepsis and AKI. Approximately 20 participants will be enrolled in the study and randomized to receive either TIN816 or placebo.

The investigator must ensure that all participants being considered for the study meet the following eligibility criteria. No additional criteria should be applied by the investigator in order to ensure that the study population will be representative of all eligible participants. Deviation from any entry criterion excludes a participant from enrollment into the study. Replacement participants may be enrolled to replace participants who discontinue the study for reasons other than safety, based on the sponsor's decision.

In the case where a safety laboratory assessment at screening is outside of the range specified below, the assessment may be repeated once prior to randomization. If the repeat value remains outside of the specified ranges, the participant is excluded from the study.

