5.2 Exclusion criteria

Participants meeting any of the following criteria at screening assessment, unless otherwise specified at randomization (Day 1) , are not eligible for inclusion in this study.

1. Not expected to survive for 24 hours.
2. Not expected to survive for 30 days due to medical conditions other than SA-AKI.
3. History of CKD with a documented estimated GFR <45 ml/min prior to development of AKI.
4. Receiving RRT or a decision has been made to initiate RRT within 24 hours of admission.
5. Weight is less than 40 kg or more than 125 kg .
6. Has life support limitations (eg, do not resuscitate, do not dialyze, do not intubate).
7. AKI diagnosis according to the AKI inclusion criteria for a period longer than 48 hours prior to study drug administration.
8. Presence of AKI for a period longer than 48 hours prior to study drug administration as suggested by clinical manifestations, e.g., prolonged oliguria or severe renal dysfunction (eg, serum creatinine > 4 mg/dL) on admission without a history of CKD.
9. Evidence of recovery from AKI based on the investigator's clinical judgement prior to randomization.
10. AKI is most likely attributable to causes other than sepsis such as nephrotoxic drugs (Non-steroidal anti-inflammatory drugs (NSAIDs), contrast, aminoglycosides), other medical conditions (e.g. heart failure, liver failure, acute abdominal aortic aneurysm, dissection, renal artery stenosis) or urinary obstruction.
11. Documented (biopsy proven) or suspected history of acute or sub-acute kidney diseases such as rapidly progressive glomerular nephritis (RPGN) and acute interstitial nephritis (AIN).
12. Patients who are post-nephrectomy.
13. Patients who are on dual antiplatelet therapy.

14. Patients who are thrombocytopenic at screening (Platelet count <100,000 microliter) or other high risk for bleeding in the opinion of the investigator.
15. Immunosuppressed patients:
 - History of immunodeficiency diseases or known HIV test positive.
 - Is receiving immunosuppressant treatment or is on chronic high doses (high-dose therapy exceeding 2 weeks of treatment) of steroids equivalent to prednisone/prednisolone 0.5 mg/kg/day, including solid organ transplant patients. Patients with septic shock treated with hydrocortisone (e.g., 3 × 100 mg) can be included.

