6.1.2 Treatment arms/group

Approximately 20 participants will be assigned at Day 1 to one of the following two treatment arms/groups in a ratio of 3:1; TIN816:placebo

- TIN816: 2 mg/kg; intravenous infusion; one-time administration
- Placebo: intravenous infusion; one-time administration

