9.1 Analysis sets

The Randomized Analysis Set (RAS) consists of all randomized participants. This analysis set will not be used for any analyses and is solely intended for providing complete information on how participants were randomized.

The PK analysis set will include all participants who survive Day 7 with at least one available valid (i.e., not flagged for exclusion) PK concentration measurement, who received complete study drug regardless of infusion duration.

The PD analysis set will include all participants with available PD data. Participants will be analyzed according to actual study treatment received.

The full analysis set (FAS) comprises all participants to whom study treatment has been assigned by randomization. According to the intent to treat principle, participants will be analyzed according to the treatment they have been assigned to during the randomization procedure. Mis-randomized participants, that is, participants who were randomized incorrectly

and did not receive any study drug will be excluded from this set. This will be the analysis set used for all efficacy analyses.

The safety set (SAF) includes all participants who received one dose of study treatment. Participants will be analyzed according to the study treatment received, where treatment received is defined as the participant took at least one dose of that study treatment regardless treatment group randomized to. This will be the analysis set used for safety analysis except for PK/PD analysis.

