2.2 Analysis sets

The Screening set (SCR) consists of all patients who have been screened. The purpose of the screening set is to describe the number of patients in screen failures. Screen failures are the patients included in the screening set but not randomized.

The Randomized Analysis Set (RAS) consists of all randomized participants. This analysis set will not be used for any analyses and is solely intended for providing complete information on how participants were randomized.

The PK analysis set will include all participants who receive treatment and survive Day 7 with at least one available valid (i.e., not flagged for exclusion) PK concentration measurement, who received complete study drug regardless of infusion duration. The PD analysis set will include all participants who receive treatment with available PD data. Participants will be analyzed according to actual study treatment received.

The full analysis set (FAS) comprises all participants to whom study treatment has been assigned by randomization. According to the intent to treat principle, participants will be analyzed according to the treatment they have been assigned to during the randomization procedure. Mis-randomized participants, that is, participants who were randomized incorrectly and did not receive any study drug will be excluded from this set. This will be the analysis set used for all efficacy analyses.

The safety set (SAF) includes all participants who received one dose of study treatment. Participants will be analyzed according to the study treatment received, where treatment received is defined as the participant took at least one dose of that study treatment regardless treatment group randomized to. This will be the analysis set used for safety analysis except for PK/PD analysis.

Immunogenicity set includes all subjects in the Safety set with a non-missing baseline anti-drug antibodies (ADA) result or at least one non-missing post-baseline ADA result.

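### Does the precision quoted for 15 TIN816 participants fail because no loss from the PK analysis set is allowed for?

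*Protocol*

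**What the plan says.** Protocol 9.9.1, repeated in SAP 3.1, states: "The proposed sample size of 15 participants in TIN816 study treatment arm is sufficient to achieve a target margin of error not larger than 15" per cent of the geometric mean, where the margin is the "half-width of a 2-sided 95% confidence interval for the PK parameters" and the GCV of AUCinf or Cmax is taken as 0.25. The same paragraph says a 1.5-fold change could be excluded if the GCV rose to 0.75. Protocol Table 9-2 and SAP Table 3-1 print interval factors of 1.15, 1.31 and 1.47 for GCVs of 0.25, 0.50 and 0.75. Their footnotes give first-in-human values at 2 mg/kg of 8% (AUCinf) and 22% (Cmax). The labels differ between the two footnotes, but the values are evidently GCVs.

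On allocation, Protocol 6.1.2 says: "Approximately 20 participants will be assigned at Day 1 to one of the following two treatment arms/groups in a ratio of 3:1; TIN816:placebo". That gives 20 × 3/4 = 15 on TIN816.

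On who is analysed, Protocol 9.1 says: "The PK analysis set will include all participants who survive Day 7 with at least one available valid" concentration, and SAP 2.2 also requires a "PK concentration measurement, who received complete study drug regardless of infusion duration". Under Protocol 8.7, AUCinf is not reported when the half-life cannot be calculated, and AUClast is used instead.

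Neither sample size section gives a loss rate, an inflation or a minimum evaluable number. Protocol section 5 (Study population) lets replacements be enrolled to "replace participants who discontinue the study for reasons other than safety, based on the sponsor" deciding.

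**The concern.** The precision is computed on everyone allocated to TIN816, while the primary analysis uses a subset. The patients are critically ill, and the protocol's own background section says: "Development of AKI in patients with sepsis is associated with significantly increased mortality rate of up to 65" per cent. The primary estimand conditions on being alive at Day 7, so the sponsor expects some early deaths, but the sample size section assumes none. AUCinf, one of the two parameters named in the claim, can be lost a second way, when the terminal phase cannot be fitted.

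Replacement is discretionary, limited to discontinuation for non-safety reasons, and not tied to the PK set. The printed factors of 1.31 and 1.47 are also not what the usual formula gives for 15, which suggests the table may not match its text.

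This is the only justification of the trial's size. If 15 evaluable participants were needed and fewer were likely, the study would be described as more precise than it is.

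**Working it through.** **Inputs.** n = 15; two-sided 95%; GCV 0.25, 0.50, 0.75; targets of 15% at GCV 0.25 and a factor below 1.5 at GCV 0.75 (all Protocol 9.9.1). First-in-human GCVs of 0.08 and 0.22 (Table 9-2 footnote).

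**Formulas.** For a log-normal parameter:
- log-scale SD: s = sqrt(ln(1 + GCV²)), which is 0.2462, 0.4724 and 0.6680 at GCV 0.25, 0.50 and 0.75
- interval factor: F = exp(t(0.975, n−1) × s / sqrt(n))
- literal half-width relative to the geometric mean: (F − 1/F) / 2

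**Reproducing the plan at n = 15.** t(0.975, 14) = 2.1448, and 2.1448 / sqrt(15) = 0.5538.
- GCV 0.25: F = exp(0.5538 × 0.2462) = 1.146; half-width = (1.146 − 1/1.146)/2 = 13.7%. The 15% claim holds on either measure.
- GCV 0.50: F = exp(0.5538 × 0.4724) = 1.299.
- GCV 0.75: F = exp(0.5538 × 0.6680) = 1.448. The 1.5-fold claim holds.

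**The printed table.** Plain n = 15 would print 1.15 / 1.30 / 1.45. The printed 1.15 / 1.31 / 1.47 match n = 14 (1.153 / 1.314 / 1.471) and also n = 15 with SD / sqrt(n−1) (1.152 / 1.311 / 1.467). The documents do not show which was used. Either way the printed factors are slightly wide, which errs on the safe side.

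**Fewer evaluable participants.**

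| n | F, GCV 0.25 | half-width, GCV 0.25 | F, GCV 0.50 | F, GCV 0.75 |
|---|---|---|---|---|
| 15 | 1.146 | 13.7% | 1.299 | 1.448 |
| 14 | 1.153 | 14.3% | 1.314 | 1.471 |
| 13 | 1.160 | 14.9% | 1.330 | 1.497 |
| 12 | 1.169 | 15.7% | 1.350 | 1.529 |
| 10 | 1.193 | 17.7% | 1.402 | 1.613 |

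The text defines the margin as a half-width. On that reading both claims hold at 13 and fail at 12, so two of 15 (13%) can be lost. If 15% instead means F − 1, the claim is narrowly missed at 14 (1.153 against 1.15). That gap disappears at the table's two-decimal rounding.

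**Room in the variability assumption.** At the first-in-human Cmax GCV of 0.22, 12 evaluable still give F = 1.148. At 0.08 (AUCinf), four give 1.136. At GCV 0.50 the factor stays below 1.5 down to n = 8 (1.484). The minimum of 13 for the 1.5-fold claim therefore belongs to the deliberately pessimistic GCV of 0.75.

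**How likely is a loss of three or more?** The documents give no rate. As an illustration only, with independent losses of an assumed 10% per participant, the chance of keeping at least 13 of 15 is 82%, and of keeping all 15 is 21%. At an assumed 20% these are 40% and 3.5%.

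**The case for a change.** The best case for a change is that the gap is real and cheap to close. Fifteen is the full allocation, the PK set is smaller by design, and nothing in the sample size text says the 15 must be evaluable. An assumed 20% loss would more likely than not leave fewer than 13, and at 12 both claims fail at the sponsor's own GCVs. Replacement does not clearly cover death, an incomplete dose or a half-life that cannot be calculated. The larger sample size mentioned under the interim analysis follows a change of dose or regimen, not lost participants. A few words and extra table rows would settle it without adding a patient.

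The missing allowance and the break-even of 13 stand. The evidence that the design will fall short does not. The 65% figure has no time window and cannot serve as a Day 7 rate. Eligibility also works against early loss: Protocol 5.2 excludes patients "Not expected to survive for 24 hours", those not expected to live 30 days because of other conditions, and those with life-support limitations. The sampling schedule (Days 2, 3, 5, 8, 14, 30, 60 and 90) gives many chances to obtain the three points after Cmax that the terminal fit requires, though later deaths would remove some of them.

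The plan also handles the consequence. SAP 2.1 reports n for PK parameters, Protocol 9.3.3 says the effect of unavailable PK data on interpretation will be considered, and Protocol 9.8 adds a second interim look at all 20 if the first gives too little PK data. A reader with the printed n, confidence level and GCVs can work out the break-even, as above.

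**Conclusion.** No change follows. Both precision claims are correct for the 15 participants they name and, with half-width taken as the text defines it, survive the loss of two. The mismatch of 1.31 and 1.47 with 1.30 and 1.45 is trivial, conservative and affects neither claim. What remains is a missing detail: the plan does not say that 15 means participants evaluable for the parameter, or that 13 is the break-even.

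Nothing the trial does or concludes depends on that detail. Protocol 9.2.1 and 9.3.2 rule out inferential analysis, no confidence interval is among the listed PK summaries, and no decision rule uses 15% or 1.5-fold. Three losses would widen the factor from 1.146 to 1.169 at GCV 0.25 and from 1.448 to 1.529 at GCV 0.75, and the reported n would show the reduced number.

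This conclusion rests on log-normal PK parameters, t-based intervals and the sponsor's GCVs of 0.25 and 0.75. The true rate of loss is unknown from the documents. If patients vary much more than assumed, precision will be worse whether or not the wording is clarified.

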10.1 Appendix 1: Regulatory, ethical, and study oversight considerations

10.1.1 Regulatory and ethical considerations

This study will be conducted in accordance with the protocol and with the following:

- Consensus ethical principles derived from international guidelines including the Declaration of Helsinki and Council for international organizations of medical sciences (CIOMS) international ethical guidelines
- Applicable ICH Good Clinical Practice (GCP) guidelines
- Applicable laws and regulations

The protocol, protocol amendments, ICF, Investigator's Brochure, [IDFU], and other relevant documents (e.g. advertisements) must be submitted to an IRB/IEC by the investigator and reviewed and approved by the IRB/IEC before the study is initiated.

Any amendments to the protocol will require IRB/IEC approval before implementation of changes made to the study design, except for changes necessary to eliminate an immediate hazard to study participants.

Protocols and any substantial amendments/modifications to the protocol will require health authority approval prior to initiation except for changes necessary to eliminate an immediate hazard to study participants.

The investigator will be responsible for the following:

- Signing a protocol signature page confirming his/her agreement to conduct the study in accordance with these documents and all of the instructions and procedures found in this protocol and to give access to all relevant data and records to Novartis monitors, auditors, Novartis Quality Assurance representatives, designated agents of Novartis, IRBs/IECs, and regulatory authorities as required
- Providing written summaries of the status of the study to the IRB/IEC annually or more frequently in accordance with the requirements, policies, and procedures established by the IRB/IEC
- Notifying the IRB/IEC of SAEs or other significant safety findings as required by IRB/IEC procedures
- Providing oversight of the conduct of the study at the site and adherence to requirements of 21 Code of Federal Regulation (CFR), ICH guidelines, the IRB/IEC, European regulation 536/2014 for clinical studies (if applicable), European Medical Device Regulation 2017/745 for clinical device research (if applicable), and all other applicable local regulations
- Inform Novartis immediately if an inspection of the clinical site is requested by a regulatory authority

This clinical study was designed and shall be implemented, executed and reported in accordance with the ICH Harmonized Tripartite Guidelines for Good Clinical Practice, with applicable

local regulations (including European Directive 2001/20/EC or European Clinical Trial Regulation 536/2014, US CFR 21), and with the ethical principles laid down in the Declaration of Helsinki.

10.1.2 Informed consent process

The investigator or his/her representative will explain the nature of the study, including the risks and benefits, to the participant or their legally authorized representative (defined as individual or judicial or other body authorized under applicable law to consent on behalf of a prospective participant to the participant's participation in the procedure(s) involved in the research) and answer all questions regarding the study.

Participants must be informed that their participation is voluntary. Participants or their legally authorized representatives will be required to sign a statement of informed consent that meets the requirements of 21 CFR 50, local regulations, ICH guidelines, privacy and data protection requirements, where applicable, and the IRB/IEC or study center.

Informed consent must be obtained before conducting any study-specific procedures (e.g. all of the procedures described in the protocol). The process of obtaining informed consent must be documented in the participant source documents.

The medical record must include a statement that written informed consent was obtained before the participant was enrolled in the study and the date the written consent was obtained. The authorized person obtaining the informed consent must also sign the ICF.

A copy of the ICF(s) must be provided to the participant or their legally authorized representative.

Eligible participants may only be included in the study after providing (witnessed, where required by law or regulation), IRB/IEC-approved informed consent.

If applicable, in cases where the participant's representative(s) gives consent (if allowed according to local requirements), the participant must be informed about the study to the extent possible given his/her level of understanding. If the participant is capable of doing so, he/she must indicate agreement by personally signing and dating the written informed consent document.

Information about common side effects already known about the investigational treatment can be found in the Investigator's Brochure (IB). This information will be included in the participant informed consent and should be discussed with the participant upon obtaining consent and also during the study as needed. Any new information regarding the safety profile of the investigational drug that is identified between IB updates will be communicated as appropriate, for example, via an investigator notification or an aggregate safety finding. New information might require an update to the informed consent and then must be discussed with the participant.

The following informed consents are included in this study:

- Main study consent Global Informed Consent
- Legal Authorized Representative consent

Both consents will also include:

- A subsection that requires a separate signature for the ‘Optional Consent for Additional Research’ to allow future research on data/samples collected during this study

A copy of the approved version of all consent forms must be provided to Novartis after IRB/IEC approval.

As per [Section 4.5](#), during a public health emergency as declared by local or regional authorities i.e. pandemic, epidemic or natural disaster, that may challenge the ability to obtain a standard written informed consent due to limits that prevent an on-site visit, investigator may conduct the informed consent discussion remotely (e.g. telephone, videoconference) if allowable by a local health authority.

Guidance issued by local regulatory bodies on this aspect prevail and must be implemented and appropriately documented (e.g. the presence of an impartial witness, sign/dating separate ICFs by trial participant and person obtaining informed consent, etc.).

